### **6.3.5. Prior/Concomitant/Follow-up medications**

*Prior medication* is defined as any medication taken before the date of the first dose of lead-in study treatment for participants who rolled over from the lead-in study and collected in this study, or before the first dose of study treatment in this study for De Novo EM participants.

*Concomitant medication* for this study is defined as any medication taken on or after the date of the first dose of open-label study treatment.

The number and percentage of participants will be tabulated by 3101-303-002 Completers from the lead-in study and De Novo EM Participants and by Anatomical Therapeutic Chemical (ATC) 4 class and preferred term (PT) for both prior medications and concomitant medications in the Safety population. Concomitant medications will be summarized by period, for the open-label treatment period and the safety follow-up period, respectively.

If a participant took a specific medication multiple times or took multiple medications within a specific therapeutic class, that participant would be counted only once for the coded drug name or therapeutic class. Any prior and concomitant medications will be included in listings.

The medication data will be coded using the World Health Organization (WHO) Drug Global B3 version March 2024 or higher.

#### **6.3.6. Adverse Events of Special Interest**

Per the 3101-306-002 Protocol Section 6.1.2, selected non-serious and serious adverse events are of special interest and will require immediate reporting, recording, and follow-up. The following events will be closely monitored:

- Treatment-emergent suicidal ideations with intent, with or without a plan, (i.e., Type 4 or 5 on the C-SSRS) or any suicidal behaviors.
- Treatment-emergent elevated ALT or AST lab value  $\geq 3 \times$  ULN.
- Potential Hy's law cases: elevated ALT or AST lab value that is  $\geq 3 \times$  ULN and an elevated total bilirubin lab value that is  $\geq 2 \times$  ULN and, at the same time, an alkaline phosphatase lab value that is  $< 2 \times$  ULN.

The summaries of above are described in the corresponding SAP Section [5.4.4.1](#) and Section [5.4.4.4](#).

#### **6.3.7. Potentially Clinically Significant Criteria for Safety Endpoints**

Laboratory values in conventional unit, the potentially clinically significant criteria for clinical laboratory parameters, Hepatic laboratory abnormalities, vital signs and ECG parameters are provided in the following sections.

### 6.3.7.1. Laboratory values in Conventional Unit

#### 6.3.7.1.1. Background

All laboratory parameters are reported in the International System (SI) units as standard practice. In addition, selected laboratory parameters (listed in [Table 6-1](#)) will be reported in conventional units to facilitate interpretation and reporting for the CSR and future labeling.

#### 6.3.7.1.2. List of Parameters Reported in Conventional Unit

The list of selected parameters required to be reported in conventional unit is provided in [Table 6-1](#).

**Table 6-1 List of Selected Parameters Reported in Conventional Unit**

Number	Laboratory Parameter	Conventional Unit	Decimal Places
1	Alanine Aminotransferase (SGPT)	U/L	0
2	Albumin	g/dL	1
3	Alkaline Phosphatase	U/L	0
4	Aspartate Aminotransferase (SGOT)	U/L	0
5	Bilirubin, Direct (Conjugated)	mg/dL	1
6	Bilirubin, Indirect (Unconjugated)	mg/dL	1
7	Bilirubin, Total	mg/dL	1
8	Blood Urea Nitrogen	mg/dL	0
9	Calcium	mg/dL	1
10	Cholesterol, HDL	mg/dL	0
11	Cholesterol, LDL	mg/dL	0
12	Cholesterol, LDL direct and calculated (combined) (This lab parameter could be the same as #11)	mg/dL	0
13	Cholesterol, Total	mg/dL	0
14	Creatine Kinase	U/L	0
15	Creatinine	mg/dL	1
16	Glucose	mg/dL	0
17	Insulin	µIU/mL	1
19	Uric Acid	mg/dL	1
20	Hemoglobin	g/dL	1

#### 6.3.7.1.3. Analysis and Reporting Format in Conventional Units

- 1) For individual clinical study reports for the central nervous system (CNS) projects, the descriptive statistics for the selected laboratory parameters ([Table 6-1](#)) will be reported in conventional units using the similar layout for the summary table in SI unit.

2) Participant narratives generated by the statistical programming team will also include the values in conventional units for the selected lab parameters ([Table 6-1](#)). That will be accomplished by presenting the values in conventional units within the parentheses next to the values in SI units. An example is provided in [Table 6-2](#) for lab parameter 'Bilirubin, Total,' for which ' $\mu\text{mol/L}$ ' is the SI unit and 'mg/dL' is the conventional unit.

**Table 6-2 Presenting Laboratory Data Using SI and Conventional Units in Narratives**

LABORATORY DATA						
Lab Test	Test Name	Normal Range		VISIT01	VISIT05	VISIT07
		Low	High	2012-07-03	2012-08-07	2012-09-04
CHEMISTRY	Bilirubin, Total ( $\mu\text{mol/L}$ (mg/dL))	0 (0)	18.81 (1.1)	6.84 (0.4)	5.13 (0.3)	5.13 (0.3)

### 6.3.7.2. Potentially Clinically Significant Criteria for Clinical Laboratory Parameters

**Table 6-3 Potentially Clinically Significant Criteria for Clinical Laboratory Parameters**

Category	Parameter	SI Unit	PCS Criteria	
			PCS Low	PCS High
Chemistry	Albumin	g/L	< 0.8 × LLN	> 1.2 × ULN
	Alanine aminotransferase	U/L	—	≥ 3.0 × ULN
	Alkaline phosphatase	U/L	—	≥ 3.0 × ULN
	Aspartate aminotransferase	U/L	—	≥ 3.0 × ULN
	Bicarbonate	mmol/L	< 0.9 × LLN	> 1.1 × ULN
	Bilirubin, total	µmol/L	—	≥ 1.5 × ULN
	Blood urea nitrogen	mmol/L	—	> 1.5 × ULN
	Calcium	mmol/L	< 0.9 × LLN	> 1.1 × ULN
	Chloride	mmol/L	< 0.9 × LLN	> 1.1 × ULN
	Cholesterol, total	mmol/L	—	> 1.6 × ULN
	Creatinine	µmol/L	—	> 1.5 × ULN
	Creatine kinase	U/L	—	> 2.0 × ULN
	Estimated glomerular filtration rate	mL/min/1.73m 	< 60	—
	Glucose, nonfasting	mmol/L	< 0.8 × LLN	> 2.0 × ULN
	Lactate dehydrogenase (LDH)	U/L	—	> 3.0 × ULN
	Phosphorus	mmol/L	< 0.9 × LLN	> 1.1 × ULN
	Potassium	mmol/L	< 0.9 × LLN	> 1.1 × ULN
	Protein, total	g/L	< 0.9 × LLN	> 1.1 × ULN
	Sodium	mmol/L	< 0.9 × LLN	> 1.1 × ULN
	Uric acid	µmol/L	—	> 1.2 × ULN
Hematology	Basophils, absolute cell count	10  /L	—	> 2.0 × ULN
	Eosinophils, absolute cell count	10  /L	—	> 2.0 × ULN
	Hematocrit	Ratio	< 0.9 × LLN	> 1.1 × ULN
	Hemoglobin	g/L	< 0.9 × LLN	> 1.1 × ULN
	Lymphocytes, absolute cell count	10  /L	< 0.7 × LLN	> 1.3 × ULN
	Monocytes, absolute cell count	10  /L	< 0.5 × LLN	> 2.0 × ULN
	Neutrophils, absolute cell count	10  /L	< 0.7 × LLN	> 1.3 × ULN
	Platelet count	10  /L	< 0.5 × LLN	> 1.5 × ULN
	Red blood cell count	10  /L	< 0.9 × LLN	> 1.1 × ULN
	White blood cell count	10  /L	< 0.9 × LLN	> 1.5 × ULN
Urinalysis	pH	pH	< 0.9 × LLN	> 1.1 × ULN
	Glucose	—	—	At least 1+
	Protein	—	—	At least 1+
	Specific gravity	—	—	> 1.1 × ULN

LLN = lower limit of normal value; ULN = upper limit of normal value; normal value provided by laboratory

SI = Le Système International d'Unités (International System of Units).

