6.1.3 Clinical Laboratory Determinations

Blood and urine samples for clinical laboratory tests will be collected at the visits outlined in [Table 1](#). Hematology, chemistry, INR, and urinalysis will be conducted at these visits. Serology and the urine drug screen will only be conducted at Visit -1 (De Novo EM Participants) and at Visit 1 (3101-303-002 Completers). The investigator will assess the clinical significance of any values outside the reference ranges provided by the central laboratory. Participants with abnormalities judged to be clinically significant, laboratory values that meet withdrawal criteria, or positive results on the urine drug screen Visit -1 or Visit 1 will be excluded/withdrawn from the study. Women of childbearing potential will be required to have a urine pregnancy test at all visits. A positive pregnancy test at Visit -1 or Visit 1 will exclude the participant from the study.

Investigators may also perform unscheduled clinical laboratory determinations at any time for the purpose of participant safety.

Participants are not required to fast overnight before coming in for their appointments.

The clinical laboratory parameters to be measured are shown in [Table 6-1](#).

Table 6-1. Clinical Laboratory Parameters

Category	Parameter
Chemistry	Sodium, potassium, chloride, bicarbonate, glucose, blood urea nitrogen, creatinine, total bilirubin, alkaline phosphatase, aspartate aminotransferase, alanine aminotransferase, lactate dehydrogenase, creatine kinase, total protein, albumin, calcium, phosphorus, uric acid, total cholesterol. The estimated glomerular filtration rate will be calculated by the central laboratory
Hematology	Hemoglobin, hematocrit, red blood cell count, red blood cell indices (mean corpuscular volume, mean corpuscular hemoglobin, mean corpuscular hemoglobin concentration), white blood cell count, including differential (neutrophils, lymphocytes, monocytes, eosinophils, and basophils), platelet count
Urinalysis	Urine dipstick for specific gravity, pH, protein, glucose, ketones, bilirubin, and blood; microscopic examination including red blood cells/high-power field, white blood cells/high-power field, and casts/low-power field
Coagulation	INR
Serology	At Visit -1 (De Novo EM Participants) and Visit 1 (3101-303-002 Completers) only: anti-hepatitis A IgM antibody, hepatitis B surface antigen, anti hepatitis C antibody, anti-hepatitis E IgM antibody.

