## 5.4. Safety Analyses

The safety analysis will be performed using descriptive statistics as described in Section 5.1 based upon the Safety population.

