#### **5.4.4. Additional Safety Assessments**

##### **5.4.4.1. Clinical Laboratory Parameters**

Descriptive statistics for values and changes from the baseline in standard (SI) units at each assessment time point will be presented for the following laboratory parameters:

Category	Parameter
Chemistry	Sodium, potassium, chloride, bicarbonate, glucose, blood urea nitrogen, creatinine, total bilirubin, alkaline phosphatase, aspartate aminotransferase, alanine aminotransferase, lactate dehydrogenase, creatine kinase, total protein, albumin, calcium, phosphorus, uric acid, total cholesterol, the estimated glomerular filtration rate
Hematology	Hemoglobin, hematocrit, red blood cell count, red blood cell indices (mean corpuscular volume, mean corpuscular hemoglobin, mean corpuscular hemoglobin concentration), white blood cell count, including differential (neutrophils, lymphocytes, monocytes, eosinophils, and basophils), platelet count
Urinalysis	Specific gravity, pH

In addition, descriptive statistics for values and changes from the baseline values in conventional units at each assessment time point will be presented for selected clinical laboratory parameters listed in [Table 6-1](#). A description of reporting the laboratory values in conventional units in participant narratives (along with the standard reporting in SI units) is presented at the end of [Table 6-2](#).

Clinical laboratory test values will be considered potentially clinically significant (PCS) if they meet either the lower-limit or higher-limit PCS criteria listed in Section [6.3.7.2](#). The number and percentage of participants who have PCS postbaseline clinical laboratory values will be tabulated. The percentages will be calculated relative to the number of participants with available non-PCS baseline values and at least 1 postbaseline assessment for the open-label treatment period. The numerator will be the total number of participants with available non-PCS baseline values and at least 1 PCS postbaseline value during the study. A supportive tabular display of participants with PCS values will be provided.

In addition, a tabular display showing all AEs that occurred in participants who had PCS postbaseline clinical laboratory values will be provided.

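### The only flagging limit for urine specific gravity, 1.1 × ULN, lies above any value urine is assumed to reach, so that row of the PCS table is zero by construction

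*SAP*

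**What the plan says.** SAP Section 6.3.7.2, Table 6-3, lists the PCS limits for laboratory parameters. The urinalysis entry for specific gravity is "Specific gravity — — > 1.1 × ULN": no unit, no low limit, and one high limit expressed as a multiple of the ULN. The footnote says that the reference limit is the "normal value provided by laboratory", so no numeric ULN is printed. Protocol Table 6-1 (Section 6.1.3) gives the method of measurement: "Urine dipstick for specific gravity, pH, protein, glucose, ketones, bilirubin, and blood".

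SAP Section 5.4.4.1 puts the limit to use. Values are PCS "if they meet either the lower-limit or higher-limit PCS criteria listed in Section" 6.3.7.2, and then "The number and percentage of participants who have PCS postbaseline clinical laboratory values will be tabulated". The numerator needs a non-PCS baseline and "at least 1 PCS postbaseline value during the study". For the denominator, "The percentages will be calculated relative to the number of participants with available non-PCS baseline values" and at least one postbaseline assessment. Two further displays follow from the flag: a supportive one of participants with PCS values, and one of all adverse events in those participants. Neither document gives another limit for specific gravity or overrides this row.

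**The concern.** A multiple of the ULN works as a margin when the scale starts at zero, as it does for an enzyme or a cell count. Specific gravity is a ratio to water, so its useful range is a short stretch above 1.000. Ten per cent of the whole value is then very large compared with that range.

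If no urine sample can exceed the limit, the tabulated count says nothing about the participants. Safety is the study's primary objective, and someone reading only the PCS table could not tell a zero that was observed from a zero that was built in. Specific gravity would also add nobody to the supportive display or to the adverse-event display.

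**Working it through.** **Inputs**

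- Multiplier: 1.1, high side only (SAP Table 6-3).
- ULN: not in the documents. Assumed 1.020 to 1.040, with 1.000 (pure water) as the limiting case.
- Highest value urine can show: not in the documents. Assumed 1.030 to 1.050, with 1.080 as a stress case.
- Reporting scale: not stated; Table 6-3 has a dash for the unit. Assumed to be the usual scale, water = 1.000.

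The plan gives a rule and no numeric cut-off, so there is no printed figure to reproduce first.

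**Step 1. The cut-off.** Limit = 1.1 × ULN. The last column is the limit's excess over water divided by the ULN's excess over water, (limit − 1)/(ULN − 1).

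| Assumed ULN | Limit | Ratio of excesses |
|---|---|---|
| 1.000 | 1.100 | not defined |
| 1.020 | 1.122 | 0.122/0.020 = 6.1 |
| 1.030 | 1.133 | 0.133/0.030 = 4.4 |
| 1.035 | 1.1385 | 0.1385/0.035 = 4.0 |
| 1.040 | 1.144 | 0.144/0.040 = 3.6 |

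What looks like a 10% margin asks for an excess over water 3.6 to 6.1 times the excess at the upper limit of normal.

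**Step 2. The reverse check.** For a urine value m to be flagged, the ULN must be below m/1.1.

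| Urine value m | ULN must be below |
|---|---|
| 1.030 | 1.030/1.1 = 0.936 |
| 1.040 | 1.040/1.1 = 0.945 |
| 1.050 | 1.050/1.1 = 0.955 |
| 1.080 | 1.080/1.1 = 0.982 |

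Every one of these is below water. The conclusion therefore does not depend on which ULN the laboratory uses, as long as it is at least 1.000.

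**Step 3. How small a working multiplier would be.** With an assumed ULN of 1.030, flagging a value just below 1.035 needs a multiplier of about 1.035/1.030 = 1.005. For a value just below 1.050 it is about 1.050/1.030 = 1.019. The table uses 1.1.

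**Step 4. The tabulated result.** No baseline value can be PCS either, so everyone with a baseline and a postbaseline reading enters the denominator N. The numerator is 0, and the row is 0/N = 0% whatever N is. Repeat or unscheduled samples, which SAP Section 6.4.4 also feeds into the PCS determination, do not change this.

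**Step 5. Sensitivity to the scale.** Reporting 1030 instead of 1.030 multiplies both sides by 1000 and changes nothing (limit 1133). Reporting only the excess over water (30 for 1.030) would give an attainable limit of 1.1 × 30 = 33, but nothing in the documents suggests that the laboratory does this.

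**The case against.** The strongest reply is that the arithmetic alone proves only that the limit is at least 1.100. That urine cannot get there rests on a physiological maximum, and on a reporting scale, that the documents do not give. This stands, and both are therefore stated as assumptions. The conclusion has room to spare: the 1.080 stress case is still 0.020 below the lowest possible limit.

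The second reply concerns consequence. A reader might infer that a safety decision depends on a broken threshold, or that urine concentration goes unmonitored. The documents support neither:

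- The withdrawal criteria (Protocol Section 8.9), the events of special interest (Protocol Section 6.1.2) and the liver discontinuation rules (Protocol Section 9.5) make no use of this limit.
- The safety analysis is descriptive throughout: "The safety analysis will be performed using descriptive statistics".
- SAP Section 5.4.4.1 names specific gravity among the parameters summarised at each time point, and SAP Section 5.1 includes the minimum and maximum, so an extreme value would show there.
- Under Protocol Section 6.1.3 the investigator assesses every value outside the central laboratory's range.
- SAP Section 6.4.4 puts all assessments in the listings.

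Two smaller objections also stand. The absence of a low limit is not an error, because many rows of Table 6-3 are high-side only (creatinine, creatine kinase and uric acid, for example). And table layouts are kept in a separate document (SAP Section 1), so we cannot see whether a row with no events would be printed at all.

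None of this makes the criterion work. Table 6-3 already drops the multiplier where it does not suit a parameter: urine glucose and protein use a dipstick grade, and estimated glomerular filtration rate uses a fixed value. Specific gravity did not get the same treatment.

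**Conclusion.** The point holds, and it is minor. Followed as written, the PCS rule for urine specific gravity flags nobody: the limit is 1.100 or higher for any ULN of at least 1.000, and 1.122 to 1.144 for an assumed ULN of 1.020 to 1.040. This rests on the assumed urine maximum (1.030 to 1.050, or 1.080 at the extreme) and on results reported with water at 1.000. Only a data or unit error, or reporting of the excess over water, could give a non-zero count.

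The size is one descriptive row, with nothing from this parameter in the two displays that depend on it. A zero there should not be read as evidence that specific gravity stayed normal. Nor should the flaw be read as a gap in participant protection or in the study's other safety summaries.

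**What to change.** Either of two changes to Table 6-3 is enough.

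1. Delete the specific gravity row and keep the by-visit descriptive summary in SAP Section 5.4.4.1. This needs no new figure, and the cost is one row less.
2. Replace the multiplier with an attainable cut-off set against the central laboratory's reference range. One form applies the multiplier to specific gravity minus 1, so that the limit is 1 + 1.1 × (ULN − 1). With an assumed ULN of 1.030 that is 1 + 1.1 × 0.030 = 1.033. This only illustrates the form; the documents do not support a particular value. Because the reading is by dipstick, confirm with the laboratory that the method can report values above whatever cut-off is chosen. The cost is a few counts of little clinical weight.

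Either way the work is one table cell and the matching program code. A bare limit of > ULN is less attractive: it would turn the row into a plain out-of-range flag, whereas the other ULN-based rows in Table 6-3 use multiples above 1.

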### 6.3.7.3. Criteria for Hepatic Laboratory Abnormalities

**Table 6-4 Criteria for Hepatic Laboratory Abnormalities**

Laboratory Parameter	Categories
ALT	$\geq 1 \times \text{ULN}$
	$\geq 1.5 \times \text{ULN}$
	$\geq 2 \times \text{ULN}$
	$\geq 3 \times \text{ULN}$
	$\geq 5 \times \text{ULN}$
	$\geq 10 \times \text{ULN}$
	$\geq 20 \times \text{ULN}$
AST	$\geq 1 \times \text{ULN}$
	$\geq 1.5 \times \text{ULN}$
	$\geq 2 \times \text{ULN}$
	$\geq 3 \times \text{ULN}$
	$\geq 5 \times \text{ULN}$
	$\geq 10 \times \text{ULN}$
	$\geq 20 \times \text{ULN}$
ALT or AST	$\geq 1 \times \text{ULN}$
	$\geq 1.5 \times \text{ULN}$
	$\geq 2 \times \text{ULN}$
	$\geq 3 \times \text{ULN}$
	$\geq 5 \times \text{ULN}$
	$\geq 10 \times \text{ULN}$
	$\geq 20 \times \text{ULN}$
Bilirubin Total	$\geq 1 \times \text{ULN}$
	$\geq 1.5 \times \text{ULN}$
	$\geq 2 \times \text{ULN}$
	$\geq 3 \times \text{ULN}$
	$\geq 5 \times \text{ULN}$
	$\geq 10 \times \text{ULN}$
	$\geq 20 \times \text{ULN}$
Alkaline Phosphatase	$\geq 1 \times \text{ULN}$
	$\geq 1.5 \times \text{ULN}$
	$\geq 2 \times \text{ULN}$
	$\geq 3 \times \text{ULN}$
	$\geq 5 \times \text{ULN}$
	$\geq 10 \times \text{ULN}$
	$\geq 20 \times \text{ULN}$
Concurrent Elevations a	ALT or AST $\geq 3 \times \text{ULN}$ and Bilirubin Total $\geq 1.5 \times \text{ULN}$
	ALT or AST $\geq 3 \times \text{ULN}$ and Bilirubin Total $\geq 2 \times \text{ULN}$
Potential Hy's Law a	ALT or AST $\geq 3 \times \text{ULN}$ and Bilirubin Total $\geq 2 \times \text{ULN}$ and ALP $< 2 \times \text{ULN}$

ALT alanine aminotransferase; AST aspartate aminotransferase; TBL total bilirubin; ALP alkaline phosphatase;  
 ULN upper limit of normal (value provided by the laboratory)

a. Elevations are from the same day.

#### 6.3.7.4. Potentially Clinically Significant Criteria for Vital Signs

**Table 6-5 Potentially Clinically Significant Criteria for Vital Signs**

Parameter	Flag	Criteria	
		Observed Value	Change from Baseline
Systolic blood pressure, mm Hg	High	$\geq 180$	Increase of $\geq 20$
	Low	$\leq 90$	Decrease of $\geq 20$
Diastolic blood pressure, mm Hg	High	$\geq 105$	Increase of $\geq 15$
	Low	$\leq 50$	Decrease of $\geq 15$
Pulse rate, bpm	High	$\geq 120$	Increase of $\geq 15$
	Low	$\leq 50$	Decrease of $\geq 15$
Weight, kg	High	—	Increase of $\geq 7\%$
	Low	—	Decrease of $\geq 7\%$
Orthostatic SBP change, mm Hg	Low	$\leq -20$	—
Orthostatic DBP change, mm Hg	Low	$\leq -15$	—
Orthostatic Pulse rate change, bpm	High	$\geq 25$	—

SBP = Systolic blood pressure; DBP = Diastolic blood pressure; bpm = beats per minute

#### 6.3.7.5. Potentially Clinically Significant Criteria for ECG parameters

**Table 6-6 Potentially Clinically Significant Criteria for ECG parameters**

Parameter	Unit	Criterion
QRS interval	msec	$\geq 150$
PR interval	msec	$\geq 250$
QTcF interval	msec	$> 500$
QTcF interval	msec	Increase from baseline $> 60$

QTcF = QT interval corrected for heart rate using the Fridericia formula

#### 6.4. Data handling convention

Day 1 is defined as day for the date of the first dose of open-label study treatment. There is no Day 0 or Week 0. Treatment day is relative to the date of the first dose of open-label study dose.

#### 6.4.1. Analysis Window

The analysis visit windows for monthly efficacy endpoints based on daily eDiary data are defined as follows:

**Table 6-7 Efficacy Analysis Visit Definitions for eDiary Data (Monthly)**

Analysis Phase	Analysis Visit (Derived)	eDiary Window
Pretreatment	Baseline	Baseline from lead-in study for 3101-303-002 Completer Last 28 days prior to treatment start date for De Novo EM Participant
Open-label Treatment Period	Weeks 1 – 4	Treatment Day [1, 28]
	Weeks 5 – 8	Treatment Day [29, 56]
	Weeks 9 – 12	Treatment Day [57, 84]
	Weeks 13 - 16	Treatment Day [85,112]
	Weeks 17 - 20	Treatment Day [113,140]
	Weeks 21 - 24	Treatment Day [141,168]
	Weeks 25 - 28	Treatment Day [169,196]
	Weeks 29 - 32	Treatment Day [197,224]
	Weeks 33 - 36	Treatment Day [225,252]
	Weeks 37 - 40	Treatment Day [253,280]
	Weeks 41 - 44	Treatment Day [281,308]
	Weeks 45 - 48	Treatment Day [309,336]
	Weeks 49 - 52	Treatment Day [337, minimum (the end of open-label treatment period, 364)]

The analysis visit windows for MSQ v2.1, PGIC, and MIDAS are defined as follows:

